10.2 Informed Consent

All study subjects are required to undergo the process of Informed Consent and sign an Institutional Review Board (IRB) approved Informed Consent Form, compliant with 21 CFR Part 50 - Protection of Human Subjects, and in accordance with institutional policies. The Informed Consent Form must be signed prior to the collection of any protocol-specific data.

Two copies of the informed consent will be made and distributed as follows: (1) the original of

A Longitudinal Outcomes Study of the Subchondroplasty Procedure in the Foot/Ankle

Protocol #: KC.CR.I.AM.16.2 version 1

the signed informed consent will be kept in the subject's file at the study site and (2) a copy will be provided to the subject.

If the Study Site does not have an IRB of record, a central IRB may be utilized upon approval by Zimmer Knee Creations.

10.3 Preoperative Procedures

All preoperative procedures are to be completed prior to the study surgery. The Schedule of Events is listed in **Table 1**.

10.3.1 The preoperative visit will include collection of basic demographic information, medical history, foot and ankle history and current use of prescription and over-the-counter pain medication.

10.3.2 The subject is to complete a series of surveys and scales regarding their clinical outcomes at the time preceding surgery, including pain, stiffness, function, and activities. These scales include:

- The Foot Function Index (FFI)
- EQ-5D
- Numeric Pain Scale

10.3.3 For subjects enrolled after the completion of the Subchondroplasty procedure, basic demographic information, medical history, foot and ankle history and pre-op use of prescription and over-the-counter pain medication data should be collected, if available, from the subject's medical record. Pre-operative FFI, EQ-5D, and/or numeric pain scale should be entered if they were collected as part of the standard of care.

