6.1 Risks of surgical intervention

With any surgical procedure, there are risks of complication including those risks currently associated with surgical interventions in the foot/ankle. These risks include intra-articular adhesions (scar tissue), superficial and/or deep wound infection, nausea and/or vomiting, bleeding, ankle pain, muscle weakness, and postoperative blood clot (hematoma). There are possibilities of wound re-opening, deep vein thrombosis (blood clot), pulmonary embolus (lung clot), vascular or nerve injury, and an allergic response to the anesthetic or medications. Some additional risks related to local anesthesia are swelling, pain, bleeding, bruising, nerve pain and loss of sensation in the skin and ligament around the foot/ankle.

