10.0 Study Procedures

10.1 Screening and Enrollment

Potential subjects will be screened from each investigator's patient population to determine if they meet the inclusion criteria described in Section 9.1 and none of the exclusion criteria described in Section 9.2. Subjects will not be invited to participate in the study until after approval of the protocol by the reviewing IRB. Subjects will be considered enrolled in the study if they meet the inclusion/exclusion criteria, sign a consent form, and undergo the SCP procedure. With prior approval of the Sponsor, the site may enroll subjects who have previously undergone Subchondroplasty. The subject will sign informed consent prior to completing follow-up study questionnaires. The Study Site will maintain a Subject Enrollment Log for all enrolled subjects.

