12.1 Relationship to study device or procedure

The relationship to the study device or procedure should be rated as follows:

- **None** (definitely not related): there is no relationship between study device or procedure and the event.
- **Possible** (remote possibility, possibly, or probably related): the relationship between study device or procedure could exist if there is no contradicting evidence that can reasonably explain the Subject's condition.
- **Definite** (definitely related): the relationship between study device or procedure and event does exist and is confirmed upon further investigation by the investigator.

- Subjects should be encouraged to report AEs spontaneously and may volunteer AE information at any time. At each evaluation, the investigator will determine whether an AE has occurred. If it is determined that an AE has occurred, the investigator should obtain all the information required to complete the appropriate AE form(s). If an event occurs at an outside institution, the investigator should attempt to obtain, if possible, required AE information to report to the Sponsor.

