14.0 Statistical Considerations and Methodology

Data collected in this study will be summarized descriptively and will be the basis of study reports. Descriptive summaries will be used to generate an overall summary of the clinical performance of the Subchondroplasty® Procedure in the foot/ankle cases and may be used for reports or to support presentations or publications.

Summaries will routinely describe categorical data as counts and percentages and ninety-five percent confidence limits will generally be used to assess categorical differences. Routine summaries describing continuous data will be in the form of means, medians, standard deviations, minima and maxima; ninety-five percent confidence intervals will be used to contrast differences. Routine summaries of return to function, patient outcomes measures, etc. will generally be described via the Kaplan-Meier method and these will generally be accompanied with the corresponding crude rates (expressed as percentages). Routine summaries of complication data will be in the form of frequencies and percentages. Summaries may be further generated for strata within the study population, (e.g., males and females, different cut-points in

the body mass index continuum, etc.). Subject confidentiality will be protected at all times and subject identifiers will not be included in study summaries.

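### For subjects enrolled after surgery, no rule says how adverse events and reoperations before consent are found, so the pooled early complication percentage may be biased low

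*Combined protocol and SAP*

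**What the plan says.** Section 10.1 opens the study to people already treated: "With prior approval of the Sponsor, the site may enroll subjects who have previously undergone Subchondroplasty". It sets no ceiling on their share of the 250 subjects and no maximum interval from surgery to consent.

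Section 10.3.3 adapts data collection for this group. It begins "For subjects enrolled after the completion of the Subchondroplasty procedure, basic demographic information, medical history, foot and ankle history and pre-op use of prescription", and the listed items "should be collected, if available, from the subject's medical record". Pre-operative FFI, EQ-5D and pain scores are added if they were part of usual care. The paragraph sits under Preoperative Procedures and names no operative, adverse-event or reoperation item.

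On consent, Section 10.2 states: "The Informed Consent Form must be signed prior to the collection of any protocol-specific data". On ascertainment of harm, Section 12.1 states: "At each evaluation, the investigator will determine whether an AE has occurred". Section 10.7 adds telephone questions about adverse events and reoperations, with no recall period.

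Other sections call for safety data without exempting late enrollees. Section 8.0 has surgical details and intra-operative safety events recorded. Section 10.4 lists intra-operative adverse events in the surgical documentation. Section 10.5 has all post-operative adverse events recorded. Table 1 marks the adverse-event form from the operative visit onward. Section 15.1 accepts medical records and operative notes as source.

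On analysis, Section 14.0 states: "Routine summaries of complication data will be in the form of frequencies and percentages". It defines no safety population, denominator or split by enrolment timing.

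**The concern.** Several of the harms that Section 6.1 names would usually appear during surgery or soon after it: "There are possibilities of wound re-opening, deep vein thrombosis (blood clot), pulmonary embolus (lung clot), vascular or nerve injury". That timing is my judgement, since the section gives none. For a subject who consents weeks or months later, this period has passed before any study evaluation takes place.

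The protocol recognises that prospective collection fails for these subjects and provides a substitute for baseline data. It provides none for post-operative events before consent. One site could abstract the whole chart while another follows Section 10.3.3 literally and takes only baseline items. With up to 25 sites, ascertainment could vary by site, and nothing in Section 14.0 would show it.

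At stake is the early complication percentage, a main safety summary of a study meant to describe clinical performance. It may combine prospectively observed subjects with others whose early period was searched to an unknown extent. Missed events can only lower it.

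**Working it through.** The plan states no complication rate, no expected share of late enrollees and no derivation of the 250, so there is no figure to reproduce. The check has two parts.

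**1. Which sections cover which period for a late enrollee**

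- Before surgery: Section 10.3.3 gives an explicit chart-retrieval rule.
- During surgery: Sections 8.0 and 10.4 and Table 1 apply generally. Operative notes normally exist and are accepted as source, so this period is largely covered, although nothing tells a site to abstract it for late enrollees.
- Surgery to consent: the general wording of Section 10.5 applies, but the mechanisms in Sections 12.1 and 10.7 run through study evaluations and calls, which have not started. No look-back is stated. This is the main gap.
- After consent: ascertainment is prospective, as for everyone else.

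**2. Possible size of the bias**

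Inputs, all assumptions except N:

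- N = 250 (Section 8.0)
- p = true risk of an early event, taken as equal in both groups
- f = share enrolled after surgery
- c = share of their pre-consent early events that is captured

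Assume complete capture in subjects consented before surgery, that the whole early period precedes consent in the others, and that all N subjects form the denominator. Then

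observed rate = (1 − f)p + f·c·p = p[1 − f(1 − c)],

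and the relative understatement is f(1 − c), whatever p is.

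With p = 5%, the expected number of events is 250 × 0.05 = 12.5. Observed rates are:

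| f | c = 0 | c = 0.5 | c = 1 |
|---|---|---|---|
| 10% | 4.50% | 4.75% | 5.00% |
| 25% | 3.75% | 4.38% | 5.00% |
| 50% | 2.50% | 3.75% | 5.00% |

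For example, at f = 25% and c = 0: 0.05 × (1 − 0.25) = 3.75%, or 9.38 of 12.5 expected events. At c = 0.5: 0.05 × (1 − 0.125) = 4.38%, or 10.94 events.

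The relative understatement is therefore 10%, 25% or 50% at c = 0, half of that at c = 0.5, and nil at c = 1. It is the same at p = 2% and p = 10%. If consent falls partway through the early period, the loss is smaller.

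Restricting the denominator to subjects consented before surgery gives N(1 − f)p / [N(1 − f)] = p, which needs no assumption about c. It estimates the risk for the whole cohort only if the two groups have equal risk.

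**The case against.** The strongest reply is that Section 10.3.3 is a sub-item of the preoperative section, so its silence on operative and adverse-event data means little. The general rules in Sections 8.0, 10.4 and 10.5 and Table 1 exempt nobody. Late enrollees come from the investigator's own patients, so charts are at hand. Telephone questions have no recall limit, subjects may volunteer events at any time, and the adverse-event form records onset date, so earlier events can be entered and dated. Section 14.0 also permits summaries by strata, which could include enrolment timing. The case report forms in Appendix C were not in the text reviewed and might carry instructions.

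Much of this stands, and it rules out several stronger readings that a reader might infer:

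- That no operative record exists for late enrollees. The general rules require one.
- That Section 10.2 blocks capture. It sets the order, consent before collection. Section 10.3.3 itself relies on looking back in the chart.
- That early harms are necessarily absent from the numerator. The text supports only that they may be incompletely captured.
- That the plan keeps late enrollees in the denominator. No denominator is defined.
- That the incidence review in Section 13.0 uses a diluted rate. That section names no denominator either.

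The objection does not supply a look-back rule. Permission to record an earlier event is not an instruction to search for it, and an optional stratified summary is not a planned one.

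**Conclusion.** The concern holds as a gap in ascertainment and reporting. The protocol does not state how adverse events and reoperations between surgery and consent are found for subjects enrolled after surgery, and it pools complication percentages with no defined denominator or split by enrolment timing. The early complication percentage may therefore be biased low.

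The relative size is f(1 − c), ranging from nil with full capture to f with none. The 10%, 25% and 50% figures are the zero-capture bound for assumed values of f, not estimates. Enrolment after surgery needs sponsor approval, so f may be small; the documents do not say. The calculation rests on equal true risk in the two groups and on late enrollees being counted in the denominator.

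A claim that early harms are missing by construction would go further than the documents allow. The matter is worth correcting because the direction is known and the remedy is cheap.

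**What to change.** 1. In Section 10.3.3 or 10.5, require sites, after consent, to complete the Surgical Documentation, Adverse Event and Surgical Reoperation forms from the medical record for the period from surgery to consent. Flag these entries as retrospectively ascertained, and record the consent date relative to surgery.
2. In Section 14.0, report intra-operative and early post-operative complication percentages separately for subjects consented before and after surgery, each with its own denominator. Make the before-surgery group the main early-harm estimate, because its ascertainment is prospective and does not depend on chart quality.

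The cost is about one sentence in each section plus some coordinator time on charts already opened for baseline items. The main early estimate has a smaller denominator: 250 × (1 − f), for example 225 at f = 10% or 125 at f = 50%. The figure may also be less favourable. Retrieved data from late enrollees are still shown, so nothing is discarded. The change affects data capture and reporting only, not clinical management.

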10.4 Subchondroplasty Procedure

All operative procedures are to be performed under aseptic conditions according to the institution's standards and following the guidelines below.

- The preoperative MRI should be used in planning the access point, trajectory and depth of the AccuPort cannula(s) for accessing the location of the BML(s).
- AccuPorts should be placed using fluoroscopic guidance.
- Use of the SCP Navigation guide is optional.
- Appropriate volume of AccuFill should be used to adequately fill the area(s) of BML(s), per the surgical technique guide in Appendix B, taking care not to over-pressurize or overfill the defect. Multiple fluoroscopic images should be taken during injection to check for extravasation of material.
- Any extravasation of material into surrounding soft tissues should be thoroughly irrigated at the time of the procedure.

The investigator is to dictate detailed operative notes that include the measures listed below, or have paper copies of the Surgical Documentation Case Report Forms completed during surgery to serve as source documents.

Surgical Documentation

- OR time
- SCP procedure time
- Anesthesia type
- Intraoperative adverse events
- Documentation of SCP injection
 - Type of AccuPort(s) used (end target, side target, gauge, etc.)
 - Volume of AccuFill injected for each lesion
- Lot numbers of SCP Complete Kit, AccuFill, AccuPort(s) and AccuMix used
- Documentation of treated BML(s)
- Concomitant procedures

10.5 Postoperative Procedures and Assessments

During the immediate postoperative period, the investigator's standard postoperative care procedures should be followed. All adverse events and complications are to be assessed and recorded on the **Adverse Event Form**, per Section 11.0 Adverse Event Reporting.

Rehabilitation should be performed per the investigator's standard of care.

10.6 Evaluation Schedule

Patients will be enrolled at the physician's office. A numeric pain score will be collected at the first post-operative standard of care visit at approximately 7-21 days. Subjects may complete follow-up questionnaires in the office, over the telephone, or online through an EDC system at the selected time points post-operatively at 6 weeks, 3 months, 6 months, 1 year and 2 years. At the 3, 4, and 5 year time points, the study coordinator will contact the subject by telephone to remind the subject to complete the numeric pain scale, the global satisfaction survey and record any revision surgeries.

If internet access is not available, questionnaires may be mailed to study subjects by their study physician at the selected time points and mailed back to their study doctor.

Follow-up evaluations are detailed in **Table 1 Schedule of Events**. Follow-up is to occur within the windows described in Table 1.

10.6.1 Any medications or therapies used for pain relief are to be recorded, specifically the classification (acupuncture, analgesic/non-narcotic, anti-inflammatory, narcotic, etc.), and whether or not the medication/therapy usage is related to the index foot/ankle. Any hyaluronic acid or cortisone injections should be recorded.

10.6.2 The subject is to complete a series of surveys and scales regarding their clinical outcomes during the time frame indicated on the form. These scales include:

- Foot Function Index (FFI)
- EQ-5D
- Numeric Pain Scale
- Subject Global Satisfaction Survey

The study database will be configured to send an email notification to subjects at the beginning of each specified visit window with a reminder that they need to complete the surveys. This email will contain a method to allow the subjects to complete their surveys electronically via the database's electronic subject reported outcomes (ePRO) system. Prior to conducting the study visit, the Study Coordinator will check to confirm whether these surveys have been completed electronically or not. If time is an issue, the Study Coordinator will fax, email or mail a copy of the surveys to the subject with instructions for completion or initiate another reminder from the ePRO system. Mailed surveys will be sent with a stamped, return envelope. The subject should be instructed to return the surveys within one week. Any subject survey forms that are not collected via the database's ePRO system are to be maintained in the subjects' study files as source documents.

10.6.3 A Subject Stipend may be offered to the subject at the completion of each follow-up time point, if in accordance with the institution's policies.

10.7 Telephone Interviews

The Study Coordinator will schedule a call with the subject within the visit window.

During the call, the subject is to be queried regarding the occurrence of any Adverse Events and Serious Adverse Events, per Section 12.0 Adverse Event Reporting. Any adverse event that results in reoperation or revision is to be recorded as a Serious Adverse Event.

The subject is to be queried regarding any reoperations of the index foot/ankle. All reoperations are to be documented using the Surgical Reoperation Form, per Section 11.1.

The subject will be reminded to complete the online surveys. The subject can also elect to complete the surveys via the telephone or mail. Any subject survey forms that are not collected via the database's ePRO system are to be maintained in the subjects' study files as source documents.

The Study Coordinator is to document the phone interview in the Telephone Log, including any completion of outcome measures via the phone.

At the 3, 4 and 5 year follow-up, the Study Coordinator will inquire about Adverse Events, Serious Adverse Events and reoperations, and remind the subject to complete the Global Satisfaction Survey and Numeric Pain Scale.

A Longitudinal Outcomes Study of the Subchondroplasty Procedure in the Foot/Ankle

Protocol #: KC.CR.I.AM.16.2 version 1

Table 1. Schedule of Events

	Visit 1	Visit 2	Visit 3	Post-Op Questionnaires	Post-Op Questionnaires	Post-Op Questionnaires	Post-Op Telephone Call
Procedures	Study Admit/ Pre- operative	Operative	SOC Post- Op Visit (7-21 days)	6 weeks	3 months 6 months	1 year 2 years	3 years 4 years 5 years
Visit Window	≤60 days Prior to Surgery			±7 Days	±14 Days	±60 Days	±60 Days
Informed Consent	X						
Inclusion & Exclusion Criteria	X						
Demographic Form	X						
Medical History	X						
Pain Medications/Therapies	X			P	P	P	
FFI	P			P	P	P	
Numeric Pain Scale	P		X	P	P	P	X
EQ-5D	P			P	P	P	
Global Satisfaction Survey				P	P	P	X
Surgical Documentation		X					
Adverse Event or Serious Adverse Event ²		(X)	(X)	(X)	(X)	(X)	(X)
Protocol Deviation ²		(X)	(X)	(X)	(X)	(X)	(X)
Telephone Contact ²				X	X	X	X
Surgical Reoperation ³			(X)	(X)	(X)	(X)	(X)
Study Exit ⁴		(X)	(X)	(X)	(X)	(X)	X

X Investigator completed forms

(X) Completed by Investigator when required

P Subject completed forms

² Case Report Forms to be completed if/when event occurs.

³ Surgical Reoperation form will be completed if the investigator performs any procedure on the index foot/ankle regardless of whether the subject's change in condition is related to the initial study procedure.

⁴ Study Exit form will be completed if the subject is no longer participating in the study for any reason.

11.0 Management of Intercurrent Events

11.1 Surgical Reoperation or Revision

A reoperation of the index foot/ankle or revision SCP injection site may be performed at the discretion of the Investigator (e.g., due to progressive pain or disability, etc.). A reoperation is defined as any surgical procedure on the index foot or ankle. For the purposes of this protocol, a revision will be defined as any partial or total joint arthroplasty or any fusion, bone fixation, bone grafting, or bone substitute procedure in the study foot or ankle.

The investigator is to dictate detailed operative notes that include the measures listed below, or have paper copies of the Surgical Reoperation Form completed during surgery to serve as a source document.

11.1.1 Surgical Reoperation Documentation

- Reason for surgery

A Longitudinal Outcomes Study of the Subchondroplasty Procedure in the Foot/Ankle

Protocol #: KC.CR.I.AM.16.2 version 1

- Postoperative diagnosis
- OR Time
- Anesthesia Type
- Status of the Subchondroplasty Injection Location

If the reoperation occurs due to an adverse event, the event should be documented on a Serious Adverse Event Form and the surgery documented on the Surgical Reoperation Form.

11.1.2 In the event that a revision occurs (defined as any partial or total joint arthroplasty or any fusion, bone fixation, bone grafting, or bone substitute procedure in the index foot/ankle), the subject will be exited from the study. A Serious Adverse Event Form and Surgical Reoperation Form will be completed.

11.1.3 In the event that a reoperation occurs that does not involve revision of the BML site(s), a Serious Adverse Event Form and Surgical Reoperation Form will be completed, and the subject will continue to be followed in the study per protocol.

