Treatment options for BMLs of the foot and/or ankle have been conservative in nature, including non-steroidal anti-inflammatory drugs, injections, calcium, physical therapy, extracorporeal shock therapy and activity modification [5, 8, 11]. Operative treatments can be joint sparing or joint destructive, however, considering the generally younger, physically active patient population with BMLs of the foot/ankle, a joint sparing procedure that does not preclude more extensive procedures in the future is desirable. Subchondroplasty[®] (SCP[®]) is a minimally-invasive procedure first described in 2007 to fill subchondral osseous defects associated with bone marrow lesions using an injectable bone substitute material (BSM), AccuFill[®] [12]. AccuFill is an injectable, self-setting, macro-porous, osteo-conductive, calcium phosphate bone graft substitute material that is intended for use to fill bony voids or gaps of the skeletal system of the extremities, spine (i.e. posterolateral spine), and the pelvis that are not intrinsic to the stability of the bony structure. These defects may be surgically created osseous defects or osseous defects created from traumatic injury to the bone. AccuFill is a bone graft substitute that resorbs and is replaced with new bone during the healing process. AccuFill has unique properties that allow it to flow through the osseous defects in trabecular bone and then set up hard at body temperature [13]. Two year results from a clinical study of the knee on 66 subjects considering total knee arthroplasty (TKA) has shown improvements in subject reported pain and function

with only 30% of subjects undergoing revision to TKA at 2 years [14]. The goal of this study is to track outcomes in a population undergoing SCP of the foot and/or ankle.

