8.0 Study Design

This is a post-market, multicenter, prospective, patient outcomes centered study to evaluate the on-label use of AccuFill during the Subchondroplasty procedure. Enrolled subjects will satisfy the inclusion/exclusion criteria and have at least one BML in any of the bones of the foot and/or ankle joint.

Demographics, medical history and medications will be recorded at the time of enrollment. Subjects will complete validated patient reported outcomes measures pre-operatively. Surgical details including the SCP® procedure, concomitant surgical procedures and intraoperative safety events will be recorded. Pain outcomes will be assessed at the first post-operative visit (7-21 days). Information on medication usage, pain, function, health status and subject global satisfaction will be collected post-operatively at approximately 6 weeks, 3 months, 6 months, 1 year, and 2 years. Subject global satisfaction and numeric pain scores will be collected at 3 years, 4 years and 5 years post-surgery. Screening for adverse events and revision surgeries will occur throughout the study. The target enrollment is 250 subjects.

Subjects will complete the study at 5 years or will be withdrawn if the patient undergoes revision of the Subchondroplasty site. For the purposes of this protocol, a revision will be defined as any joint arthroplasty, fusion or any bone fixation, bone grafting or bone substitute procedure on the index foot/ankle.

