11.7 Withdrawal and Study Re-Entry

During the course of the study, it is possible that subjects will be withdrawn from the study. Factors leading to subject withdrawal may include, but are not limited to, the following:

Subject Withdrawal – A subject may voluntarily withdraw from the study at any time without prejudice or affecting their future medical treatment. Investigators may withdraw a subject due to non-compliance with the protocol or follow-up questionnaire schedule, or for any other reason per their professional opinion. The date and reason for subject withdrawal is to be documented on the **Study Exit** form.

If a subject is withdrawn or terminated due to medical safety considerations because of an adverse event, the adverse event must be followed by the investigator to satisfactory resolution or until the investigator determines the event to be chronic or clinically stable. All study data related to event is to be recorded.

Subject Lost to Follow-Up – If the subject does not complete the required questionnaires and the Investigator or Study Coordinator has attempted to contact that subject at least three times via telephone and receives no response, the subject may be deemed to be lost to follow-up. The research staff will document the attempts to contact the subject. The final attempt to contact the subject will be performed by register/return receipt mail. The receipt will be placed in the

subject's binder. A study Exit Form must be completed.

Should a subject who previously chose to withdraw or was considered lost-to-follow-up wishes to re-enter the study, a new Informed Consent will be required. The site may resume scheduled follow-up visits from the subject's last follow-up visit.

Subject Death – Should a subject expire, complete the Adverse Event and Study Exit Form. Submit copies of the death certificate, autopsy report (if applicable and available) and source documents related to the death. The Investigator will make written notification to the IRB upon the death of a subject in the study.

When a subject withdraws or is withdrawn, all study procedures completed and data collected prior to the date of withdrawal will be submitted to the sponsor and included in the study database, unless the subject requests otherwise in writing.

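### Subjects leave the study at revision and Section 14 does not count revision as an unfavourable result, so later outcome summaries describe unrevised subjects only and will tend to flatter the procedure

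*Combined protocol and SAP*

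**What the plan says.** Section 8.0 sets the rule: "Subjects will complete the study at 5 years or will be withdrawn if the patient undergoes revision of the Subchondroplasty site". Section 11.1.2 repeats it: after a revision, "the subject will be exited from the study", with a Serious Adverse Event Form and a Surgical Reoperation Form completed.

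The definition is broad. Section 11.1 counts any partial or total arthroplasty, any fusion, and any "bone fixation, bone grafting, or bone substitute procedure in the study foot or ankle", so it is not confined to the treated lesion. The same section gives an example of why further surgery may be done: "due to progressive pain or disability, etc". Under Section 11.1.3, if a reoperation does not revise the lesion site, "the subject will continue to be followed in the study per protocol".

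Data from before exit are kept. Section 11.7 states that "all study procedures completed and data collected prior to the date of withdrawal will be submitted to the sponsor and included in the study database". A written request from the subject can override this.

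Follow-up has two tiers (Section 8.0 and Table 1). From 6 weeks to 2 years, "Information on medication usage, pain, function, health status and subject global satisfaction will be collected post-operatively". At 3, 4 and 5 years only the pain score and satisfaction are collected.

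Section 14.0 is the whole analysis plan. Continuous data get means, medians, standard deviations and ranges, and categorical data get counts and percentages. Return to function and patient-reported measures are generally described by Kaplan-Meier with crude rates alongside, and complications by frequencies. It names no analysis population, no missing-data rule, no treatment of revision, and no event or censoring definition for Kaplan-Meier.

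**The concern.** Pain and function are study outcomes, and worsening pain or disability is the protocol's own example of a reason to reoperate or revise. Leaving the study at revision is therefore related to the outcome being measured. If each visit is summarised over the subjects who still supply data, the less successful cases drop out progressively and the later visits look better for that reason alone.

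Kaplan-Meier does not remove the problem. If the event is improvement or return to function and exit at revision is handled as ordinary censoring, the method assumes that revised subjects had the same prospects of improving as those still followed. That assumption is hard to defend here, and its failure raises the estimated proportion improved.

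The study has one arm and is purely descriptive, and Section 14.0 intends these summaries to stand as the account of clinical performance in reports and publications. No comparator would reveal the distortion.

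**Working it through.** The plan derives no figure on this point: 250 is a stated target without a calculation, and no foot/ankle revision rate appears. There is nothing to reproduce, so the following illustrates size.

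**Inputs**
- N = 250: target enrolment, Section 8.0.
- r, share revised by a late visit: assumed 5% to 30%. The top is the only revision rate in the documents, from 66 knee subjects considering total knee arthroplasty (Section 5.1): "with only 30% of subjects undergoing revision to TKA at 2 years".
- p, success (for example, satisfied) among unrevised subjects: assumed 70%.
- d, how much worse revised subjects would score on the pain scale: assumed 1 to 3 points.
- No other loss to follow-up.

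**Success proportion.** With revision counted as non-success, success among all treated = p × (1 − r). Overstatement = p − p(1 − r) = p × r. For scale, the 95% half-width of the unrevised-only estimate is 1.96 × √[p(1 − p)/n], with n = 250(1 − r). At r = 10% this is 1.96 × √(0.70 × 0.30/225) = 0.060.

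| r | Exited | n left | Success, all treated | Overstatement (points) | Half-width (points) |
|---|---|---|---|---|---|
| 5% | 12.5 | 237.5 | 66.5% | 3.5 | 5.8 |
| 10% | 25 | 225 | 63.0% | 7.0 | 6.0 |
| 20% | 50 | 200 | 56.0% | 14.0 | 6.4 |
| 30% | 75 | 175 | 49.0% | 21.0 | 6.8 |

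The bias passes sampling error by about 10% revised and is below it at 5%. The choice of p matters moderately: for p = 60%, p × r runs from 3 to 18 points, and for p = 90%, from 4.5 to 27.

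**Mean pain.** All-treated mean minus unrevised mean = r × d. The smallest case is 0.05 × 1 = 0.05 points and the largest is 0.30 × 3 = 0.9. With d = 2 the shift is 0.1, 0.2, 0.4 and 0.6 points at r = 5%, 10%, 20% and 30%.

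**Which procedures lead to exit.** Setting the rules side by side shows that they conflict:
- Section 8.0 withdraws for revision of the treated site, then defines revision as any listed procedure on the index foot/ankle.
- Section 11.1.2 exits on the broad definition.
- Section 11.1.3 keeps subjects whose reoperation does not revise the lesion site.
- Section 11.3 allows exit only under Section 11.7, whose list is open-ended but does not name revision.

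A fusion elsewhere in the index foot fits both 11.1.2 and 11.1.3, so the number exited depends on which rule a site applies.

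**The case against.** The strongest reply is that Section 14.0 is silent rather than wrong. Each revision is recorded on two forms, data before exit are kept, complications are tabulated and Kaplan-Meier is planned, so an analyst could still count revision properly. It is also reasonable to stop questionnaires after a fusion or arthroplasty, because later scores reflect the second operation. The study is post-market and descriptive, with no hypothesis test.

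Much of this stands. The retained data are what make the correction cheap, and stopping questionnaires is a defensible choice. But silence is not neutral: once subjects have been exited, a plain visit mean or percentage can only cover those who remain.

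A reader might infer more than the documents support:
- *That only successes remain.* Unrevised subjects with persistent pain stay in, as do those with a reoperation that spares the lesion site. Some exits may concern another part of the foot and need not mean that the treated site failed.
- *That revised subjects disappear altogether.* Their earlier data and the revision itself are retained.
- *That function is affected to 5 years.* The Foot Function Index stops at 2 years. Conversely, visits before 1 year are affected too.
- *That safety follow-up ends.* Section 12.4 follows serious adverse events until they resolve or are judged chronic or stable. What is lost is routine screening for new events after exit.
- *That the bias is known to be large.* The 30% comes from the knee, and Section 5.1 itself says foot/ankle lesions differ in presentation and course.

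**Conclusion.** The point holds as a bias of predictable direction and unknown size. Exit at revision is mandatory, it is plausibly linked to poor outcome by the protocol's own example, and nothing in Section 14.0 counts it as unfavourable. Observed-case summaries after that point describe unrevised subjects and will tend to look better than the treated cohort. Kaplan-Meier estimates err in the same direction if exit is treated as non-informative censoring.

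Under the assumed 5% to 30% revised and 70% success among the unrevised, the overstatement is 3.5 to 21 points. It is negligible relative to sampling error only if revision is rare. The shift in mean pain is smaller, 0.05 to 0.9 points for an assumed gap of 1 to 3 points. The revision rate, the 70% and the pain gap are all assumptions.

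**What to change.** Amend Section 14.0, using data already collected:

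1. For responder and satisfaction summaries, keep all treated subjects due at the visit in the denominator. Count a revised subject as not a success from the revision date, and state the threshold for improvement.
2. In Kaplan-Meier summaries of return to function or improvement, define the event, and treat revision as a failure or competing event rather than as non-informative censoring.
3. Report the cumulative incidence of revision with a 95% confidence interval, split into the treated site and elsewhere in the index foot/ankle.
4. Label visit means as unrevised subjects and show the cumulative number revised beside each n.

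Separately, Sections 8.0, 11.1.2, 11.1.3 and 11.3 must be reconciled on which procedures lead to exit.

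The cost is wording and analysis programming. The downside is that reported success becomes less favourable and that some revisions away from the treated site count as non-success, which the split in item 3 makes visible. Continuing follow-up after revision is optional. It would need a protocol amendment with IRB approval (Section 11.4), and the scores would partly reflect the second operation.
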